ClinicalTrials.gov ID: NCT05370326

Title: Feasibility and Preliminary Efficacy of an Opioid Stewardship Program in Hospitalized Patients With Chronic Pain

Document: Protocol with SAP

Date: 5/4/2022

CLINICAL STUDY PROTOCOL

Observational Study of Individual or Group Template

Randomized Controlled Pilot Trial to Evaluate Feasibility and Preliminary Efficacy of an Opioid Stewardship Program in Hospitalized Patients with Chronic Pain

Protocol Number

Yale HIC#2000032638

Protocol Version

April 2022

1

Confidentiality Statement:

Synopsis

Purpose

The purpose of this work is to investigate the feasibility and preliminary efficacy of an enhanced opioid stewardship program, tailored to the needs of hospitalized patients with chronic pain with opioid dependence, incorporating real-time guidance from an addiction medicine and pain-trained physician/pharmacist team, using a pilot randomized clinical trial format. Findings from this research may improve pain management and decrease risk of opioid-related adverse events among patients with chronic pain.

Primary Objective

The primary objective of this study is to determine whether an enhanced opioid stewardship program, tailored to the needs of patients with chronic pain, is feasible to implement in a hospital setting.

Secondary Objective

One secondary objective is to determine whether an enhanced opioid stewardship program increases use of guideline-based opioid care. The other secondary objective of this study is to determine whether an enhanced opioid stewardship program reduces pain frequency, intensity, and interference and decreases the risk for opioid-related adverse events among adult patients with chronic pain hospitalized on medical units at Yale-New Haven Hospital, York Street and Saint Raphael campuses.

Study Design

We propose a pilot randomized controlled trial of 100 adult patients hospitalized on medicine units at Yale-New Haven Hospital York Street Campus and Saint Raphael campus. The trial will be prospective and focus primarily on feasibility.

Study Date Range and Duration

The study will commence upon IRB approval. The duration of participation for each study subject will include days in the hospital from study enrollment to discharge and 30 days after discharge. Therefore, the minimum duration of the study is 30 days.

Number of Study Sites

The study will take place at one site: Yale New Haven Hospital (YSC and SRC).

Primary Outcome Variables

The primary outcomes for this pilot RCT will relate to feasibility of recruitment and retention. For recruitment, we will describe the number of patients screened vs. the number of patients eligible; the number of patients eligible vs. the number enrolled; and the hospital day of enrollment (in relation to the admission and discharge dates). For retention, we will describe the number of participants in the intervention group for whom

we are able to deliver the full enhanced opioid stewardship intervention, as well as the number in intervention and control groups who complete the peri-discharge evaluation.

Secondary and Exploratory Outcome Variables (if applicable)

A secondary outcome for this pilot RCT will include a count of guideline-based care elements considered to be “best practices” for opioid stewardship in the setting of chronic pain. These include ordering of alternative pain relief medications (e.g., acetaminophen), ordering of a bowel regimen, ordering of medication to treat opioid use disorder, order of urine toxicology screen, ordering of ECG for patients prescribed methadone, avoidance of co-prescriptions of benzodiazepines, and other associate “best care” practices. These metrics will be abstracted from the medical record.

Other secondary outcomes will include pain frequency, intensity, and interference, assessed using a modified Brief Pain Inventory.¹ Depression and anxiety will be measured using the Patient Health Questionnaire-4.² Participant satisfaction with pain care will also be assessed at discharge. ED visits and readmissions at the 30 days post-discharge from the hospitalization in which the participant is recruited will also be abstracted from the medical record.

Study Population

The study population will be comprised of adult patients (≥ 18 years) hospitalized on medical units at YNHH YSC and SRC with chronic pain and opioid use. Eligible patients can be hospitalized for any medical condition (i.e., admission diagnoses do not need to be related to chronic pain). Patients will be identified by a pre-specified case identification tool (i.e., Epic report).

Number of Participants

We will enroll 100 participants for this feasibility study.

Study Schedule

The total number of visits as part of this intervention will include (1) screening and consent, (2) baseline interview (may be combined with consent visit, per participant’s preference), and (3) a peri-discharge interview (within 48 hours of anticipated discharge). The total number of study visits is expected to be three per participant, with the potential for greater frequency of interaction via phone. Each visit will last approximately 30 minutes or less.

Protocol Revision History

Version Date	Summary of Substantial Changes

Statement of Compliance

This document is a protocol for a human research study. The purpose of this protocol is to ensure that this study is to be conducted according to the Common Rule at 45CFR46 (human subjects) and other applicable government regulations and Institutional research policies and procedures.

Abbreviations

Abbreviation	Explanation
--------------	-------------

CP: chronic pain

MOUD: medications to treat opioid use disorder

OUD: opioid use disorder

Table of Contents

1. Background	7
2. Study Purpose and Objectives	11
3. Study Design	12
4. Study Methods/Procedures	13
5. Trial Administration	17
Appendices	22
References	23

1 Background/Literature Review

1.1 Background

Many patients with CP who receive long term opioid therapy will experience opioid dependence and are at risk for opioid-related harms, including opioid use disorder (OUD). Hospitalizations of patients with CP and opioid dependence are increasing nationally³ and are an important opportunity to optimize the use of medications for CP and OUD, when indicated. Hospitalizations can also be risky for this patient population, as opioids are the second most common cause of preventable adverse events in hospitalized patients.⁴ Administration of opioids and other controlled substances such as benzodiazepines contribute to new episodes of or higher dosages of long-term opioids after hospital discharge. Notably, there has been increased recognition of the “stress of hospitalization,” including sleep deprivation, immobility, and uncertainty about care plans.⁵ This stress may exacerbate CP, anxiety and depression. Our work has demonstrated that generalist prescribers rarely follow opioid prescribing guidelines⁶⁻⁸ and most prescribing decisions regarding CP and opioid dependence during hospitalization are made by clinicians with limiting training in the management of these conditions. As a result, front-line hospital prescribers often do not prescribe opioids and other controlled substances according to best practices for patients with CP and opioid dependence, with or without OUD. While addiction consult services are growing, they are not always involved in the care of patients with CP and are limited to a small number of academic medical centers.

Recently “opioid stewardship” programs, modelled after “antibiotic stewardship” programs that manage the adverse individual and public health effects of antibiotic prescribing that does not adhere to guidelines, have been created by hospitals to improve opioid prescribing in the hospital setting.^{4,9} These programs, endorsed by the Joint Commission (the entity that accredits hospitals nationally), bring focused expertise to promote the appropriate use of opioids and improve patient outcomes. They are consistent with the Joint Commission’s mandate in 2018 for hospitals to implement leadership teams and performance improvement processes to address opioid prescribing. However, a 2020 survey of hospitals reported that only 14% prospectively identified patients in need of stewardship services – the model we propose.⁴ Prospective opioid stewardship programs vary by hospital but typically use automated case finding to identify eligible patients and then implement medication and non-medication treatments balancing opioid risks, often assessed as milligram morphine equivalents (MMEs), and benefits, often assessed using measures of pain and pain interference.

While there is growing use of hospital-based opioid stewardship programs, they have not been tailored to the needs of patients with CP and opioid dependence, with or without OUD. Hospitalized patients with CP and opioid dependence, and the clinicians who care for them, face a range of key decisions regarding each condition. For instance, the management of methadone, buprenorphine and naltrexone for patients with OUD involves clinical considerations including important patient preferences. Additionally, hospitalized patients with CP and opioid dependence can experience both acute pain from injury, surgery or medical procedures as well as exacerbations of CP during hospitalization that require tailored treatment. Clinical decisions about which medication and non-medication-based pain treatments to deploy involve weighing risks and benefits, including the impact of treatments on OUD and comorbid anxiety and depression. These decisions, especially those related to medications, may have important consequences with respect to CP, opioid dependence with or without OUD, anxiety, depression and health care utilization. There are few published studies to inform stakeholders regarding the efficacy of hospital-based opioid stewardship, especially in patients with CP and opioid dependence.

The Yale-New Haven Hospital System has implemented an opioid stewardship program, modelled after “antibiotic stewardship” programs that manage the adverse

individual and public health effects of antibiotic prescribing, to improve opioid prescribing in the hospital setting.⁴ This program, endorsed by the Joint Commission, brings focused expertise to promote the appropriate use of opioids and improve patient outcomes through opioid use monitoring and development of “best practice” recommendations regarding opioid prescribing. However, the YNHHS Opioid Stewardship Program has limited impact on the care of individual patients, as the only patient-specific intervention implemented is the delivery of automated “best practice alerts” (i.e., “pop-ups”) through the electronic medical record of clinicians.

The purpose of the proposed study is to evaluate the feasibility and preliminary efficacy of an opioid stewardship program that provides real-time interaction and guidance from an addiction medicine and pain-trained physician/pharmacist team, focusing on implementing and tailoring best practices for use of opioids for patients hospitalized with CP and opioid dependence. We propose to evaluate the implementation and assess preliminary efficacy of the intervention.

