1.5.2 Potential Benefits

Participants in this pilot RCT may potentially derive certain benefits, although none are guaranteed. Immediate potential benefits include improved pain management, including decreased severity or frequency of pain, and reduced interference from pain in going about daily activities. Another immediate potential benefit would be reduced risk of opioid-related adverse events during hospitalization, including over-sedation, gastrointestinal side effects, as well as identification of an opioid use disorder, leading to treatment consistent with usual care (which would be recommended by the intervention team). Potential long-term benefits include decreased risk of developing OUD or improved treatment of an existing OUD, and better pain management and quality of life. These benefits would apply primarily to the intervention group. The control group will be treated with usual hospital-based care.

2 Study Purpose and Objectives

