3.3.1 Number of Participants

We anticipate 10-50 records will be returned in the Epic report each day that will be screened for eligibility. We aim to recruit 100 participants who meet all inclusion and exclusion criteria for the trial, for a total of approximately 50 each in the intervention and control arms. Screening and enrollment will continue until the target sample size has been reached, with a goal of recruiting 5-10 patients per week.

Eligibility Criteria/Vulnerable Populations

In order to be eligible for inclusion in the study, an individual must meet all of the following criteria:

- adults (age ≥ 18 years);
- admitted at YNHH (YS and SRC) on medical units;
- identified as having chronic pain and prescribed opioids.
- Have opioid dependence (evidenced by ongoing opioid prescription, meeting DSM-5 criteria for OUD, or clinical history)

Any individual who meets any of the following criteria will be excluded from participation in this study:

- active cancer
- current pregnancy
- hospice care/comfort measures only
- admission to inpatient psychiatry
- completed or planned Addiction Medicine consult during hospitalization

4. Study Methods/Procedures

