3.4 Study Procedures

All patients will receive standard hospital care. Patients who are identified as eligible for the study via screening in Epic will be approached during hospitalization, undergo informed consent, and be enrolled in the study. Those who consent will be asked questionnaires

related to patient reported outcomes of pain, anxiety, depression and quality of life at baseline. Patients will then be randomized on a 1:1 ratio to either the enhanced opioid stewardship program arm or a control (i.e., usual care) arm. Patients who are randomized to the intervention arm will have their medical record reviewed by both a pharmacist and a physician trained in pain and addiction medicine. The pharmacist and physician will provide best practice guidance via an Epic note to the primary care teams to consider, versus continuation with their usual care plan. All guidance will be voluntary for clinical teams to follow. All participants will be tracked daily in Epic for discharge status, and when discharge within 48 hours is anticipated, the study team will perform the final patient interview, which will be very similar to the baseline interview and composed of questionnaires related to pain, anxiety, depression, and quality of life. Medical record abstraction will be performed to abstract relevant characteristics of each participant's hospitalization, use of guideline-based best practices for pain management and opioid stewardship at discharge, and incidence of readmissions and ED visits within 30 days after discharge for the hospitalization during which the participant was recruited.

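### OUD status is not recorded uniformly before randomization, although one item of the guideline-care count depends on it; one entry field and one named covariate would close the gap

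*Combined protocol and SAP*

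**What the plan says.** - **Population.** The eligibility criteria under Section 3.3.1 require opioid dependence, "evidenced by ongoing opioid prescription, meeting DSM-5 criteria for OUD, or clinical history". Only the second of these three grounds establishes OUD, so both kinds of patient are enrolled. The background (Section 1.1) has the same mixed population in view when it says of existing programs that "they have not been tailored to the needs of patients with CP and opioid dependence, with or without OUD".
- **Allocation.** Section 3.4: "Patients will then be randomized on a 1:1 ratio". No stratification factor is named. The target is 100, "for a total of approximately 50 each in the intervention and control arms" (Section 3.3.1).
- **Outcome.** Section 3.2.2 names six elements of the guideline-care count. One is an order for OUD medication.
- **Data before randomization.** The baseline interview (Section 3.6.3) covers pain, PHQ-4 and demographics. The screening chart review (Section 3.6.1) is described as checking that no exclusion applies. The abstraction of hospitalization data and care practices is scheduled 1-30 days after discharge (Section 3.5).
- **Analysis.** Sections 3.7.1 and 3.7.3 rely mainly on unadjusted bivariate tests. Covariate balance is examined, and exploratory regression is allowed, chiefly if an imbalance turns up. No covariate is named.
- **OUD found during the trial.** Section 1.5.2 lists among the possible benefits "identification of an opioid use disorder, leading to treatment consistent with usual care (which would be recommended by the intervention team", and says that the benefits fall mainly to the intervention group.

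**The concern.** The OUD-medication item ties the guideline-care count to OUD status by its own wording: a patient without OUD has no occasion for that order. If the arms differ by chance in their share of OUD patients, part of any difference in the count reflects case mix. Even without a visible gap, an omitted prognostic factor leaves variance in the estimate that could be removed at almost no cost.

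Timing is the more important part. The plan's answer to imbalance is to look for it and then perhaps adjust. That needs a value of OUD status that the intervention could not have influenced. The listed chart abstraction comes after discharge. By then the study physician has written a note in the records of intervention participants only, and the program may have led to OUD being recognized in that arm. Adjusting for, or subgrouping by, a status that depends on arm can introduce bias where randomization had left none. After the trial, a clean variable may be hard to recover.

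At stake is the precision and readability of one secondary efficacy contrast that is meant to feed a manuscript and grant applications (Section 4.15).

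**Working it through.** The plan offers no calculation to reproduce. Section 3.7.2 declines a power calculation, and no SD, effect size or OUD share is given. The only arithmetic, 100 at 1:1 = 50 + 50, agrees.

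**Inputs.** From the protocol: n = 50 per arm. Assumed, because the documents are silent: OUD share p = 0.1 to 0.5; SD of the care count 1.0 to 1.5; shift in the count due to OUD, d = 0.5 or 1 element; simple randomization; two-sided 5% level.

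**1. Chance imbalance.** The difference in OUD share is taken as that of two independent Binomial(50, p) counts, with SD = √(2p(1−p)/50). A gap of 10 points is 5 patients; 20 points is 10 patients.

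| p | SD of gap (points) | P(gap ≥ 10 points) | P(gap ≥ 20 points) |
|---|---|---|---|
| 0.1 | 6.0 | 13.1% | 0.2% |
| 0.2 | 8.0 | 25.9% | 1.7% |
| 0.3 | 9.2 | 32.6% | 3.8% |
| 0.4 | 9.8 | 35.8% | 5.2% |
| 0.5 | 10.0 | 36.8% | 5.7% |

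Holding the total number of OUD patients fixed (hypergeometric) gives 9-32% for 10 points or more.

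**2. What a 10-point gap does.** It shifts the unadjusted difference by 0.1 × d, which is 0.05 element (d = 0.5) or 0.10 element (d = 1). The standard error is SD × √(2/50) = 0.2 × SD, or 0.2 to 0.3 element. The shift is therefore between 0.05/0.3 = 0.17 and 0.10/0.2 = 0.5 of a standard error.

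**3. Precision gained by adjusting.** The variance removed is p(1−p)d²/SD², and the interval width is multiplied by √(1 − that).
- d = 0.5, smallest case (p = 0.1, SD 1.5): 0.09 × 0.25/2.25 = 0.010; √0.990 = 0.995, a gain of 0.5%.
- d = 0.5, largest case (p = 0.5, SD 1.0): 0.25 × 0.25/1 = 0.0625; √0.9375 = 0.968, a gain of 3.2%.
- d = 1, smallest case: 0.09 × 1/2.25 = 0.040; √0.960 = 0.980, a gain of 2.0%.
- d = 1, largest case: 0.25 × 1/1 = 0.25; √0.75 = 0.866, a gain of 13.4%.

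The formula ignores the degree of freedom that the covariate uses, so the bottom of the range is in practice no gain.

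**4. Type I error.** Averaged over randomizations, the unadjusted test keeps its 5%. Given a 10-point gap it is 5-6%. Given a 20-point gap it is about 7% if OUD shifts the outcome by 0.5 within-stratum SD, and 12-13% if by 1.0 (p = 0.2 to 0.5). Step 1 shows that gaps of that size are uncommon.

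**5. The imbalance trigger.** A 5% balance test would respond only to a gap of about 1.96 × SD: 1.96 × 6.0 = 11.8 points up to 1.96 × 10.0 = 19.6 points. Most gaps of 10 points or a little more would pass unnoticed.

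**The case against.** This is a feasibility pilot. Its primary outcomes concern recruitment and retention, it disclaims power, and its objectives ask nothing by OUD status. The balance check and optional regression are a real, if partial, safeguard. The OUD share may be low, because the criteria exclude anyone with a "completed or planned Addiction Medicine consult during hospitalization"; at 10%, a gap of 10 points or more occurs in only 13% of randomizations. A full-element shift is about the most that the OUD-medication item alone could produce: every OUD patient would need the order. That is unlikely under usual care, which Section 1.1 describes as seldom following guidelines. Baseline pain or campus could be proposed as covariates on similar grounds. A diagnosis dated before randomization might still be found in the chart later. And a charted field would miss the unrecognized OUD that the program is expected to find.

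Most of this stands, and it limits the point to a cheap improvement. It does not remove it. The balance check names no covariate and responds only to sizeable gaps. OUD has a claim that the other candidates lack, since an item of the outcome is defined by it. Later recovery of a dated diagnosis is possible but not planned, and it would be done with the intervention note already in one arm's charts. Imperfect charting dilutes the gain, but a status fixed before allocation cannot be affected by arm.

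**Conclusion.** The point holds as a low-cost improvement to one secondary analysis. OUD status enters neither the allocation nor any committed analysis, no uniform record of it before randomization is listed, and a record made after discharge would not be a safe substitute. On the assumed ranges above, the interval for the care count would narrow by about 0.5-3% (shift of 0.5 element) or 2-13% (shift of 1 element).

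Three stronger readings are tempting but not supported:
- **That every efficacy contrast is blurred.** The documents give no link between OUD and the size of pain scores, PHQ-4, satisfaction or 30-day returns. The background says only that treatment decisions may affect such outcomes. The documented route is the one item of the care count.
- **That the trial is biased.** Chance imbalance is not bias on average. The unadjusted standard error already includes it, and overall type I error is kept.
- **That the protocol treats OUD as the main divide, so the pilot should establish whether the effect differs by OUD.** Sections 1.1 and 1.3 give OUD medication as one example among several decisions. At a 20% share there would be about 10 OUD patients per arm, too few for more than description.

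The primary feasibility outcomes do not change.

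**What to change.** - Add one yes/no REDCap field, *OUD at entry (DSM-5 or charted diagnosis)*, completed for every participant during the eligibility chart review and locked before randomization.
- Add one sentence to Section 3.7.3: the between-arm estimate of the guideline-care count will be adjusted for this field, whatever the observed balance. OUD first recorded after randomization will not be used as a covariate or subgroup.
- The same covariate for pain and 30-day returns is reasonable, but it rests on an assumed association, and the plan should say so.
- Stratifying the 1:1 list by the field, blocked within strata, is optional. Results by OUD at entry should be descriptive only.

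The cost is one screening field and one analysis sentence, with no extra patients or visits. The downside is that charted OUD is imperfect and misses unrecognized cases, which reduces the gain.
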